#### Part 1: Selection phase

The randomized section of this study started with the following three initial combination arms among which eligible subjects will be randomized with equal probability:

- **Arm 1:** LAG525 600 mg i.v. Q4W and spartalizumab 400 mg i.v. Q4W
  - Declared futile at interim analysis 2

- **Arm 2:** capmatinib 400 mg p.o BID and spartalizumab 400 mg i.v. Q4W
  - Declared futile at interim analysis 1
- **Arm 3:** canakinumab 300 mg s.c. Q4W and spartalizumab 400 mg i.v. Q4W
  - Declared futile at interim analysis 1

With protocol amendment 3, a fourth combination arm (Arm 4) was added:

- **Arm 4:** ribociclib 600 mg p.o QD on Days 1 to 21 of a 28-day cycle and spartalizumab 400 mg i.v. Q4W
  - Declared futile at interim analysis 3

After approval of protocol amendment 3 at each respective study site, eligible subjects will be randomized with equal probability across any of the four arms that are still open to enrollment within the selection phase.

As dose regimens for additional new combinations with spartalizumab become established, new combination arms will be added under the same master protocol through protocol amendments. A maximum of 10 arms may be active (open to enrollment) at any given time under this master protocol, and any arms active in part 1 will continue to be randomized with equal probability.

At each interim analysis, it will be determined which arm(s) (1) is declared efficacious and will be expanded to part 2, (2) will continue enrollment in part 1 (up to a maximum of 45 subjects enrolled in a given arm) or (3) will be dropped for futility, taking into account all available efficacy, safety and biomarker data. If a combination arm can be expanded to part 2, the exact sample size for part 2 will be determined at that time when the decision to expand this arm is taken (refer to [Section 10.8.1](#) for further details on sample size considerations). The timing of interim analyses and the criteria used for decision-making at each interim analysis are detailed in [Section 4.2.1](#) and [Section 10](#).

The maximum sample size for the first four arms in part 1 is approximately 180 subjects. However, based on simulations of sample size detailed in [Section 10.8.1](#), it is expected that approximately 92-121 subjects will be enrolled in the first four arms during the selection phase.

Arm 1 (LAG525 plus spartalizumab) did not meet the efficacy nor the futility criterion at interim analysis 1, and enrollment was continued until the maximum of 45 subjects were randomized, and the arm was declared futile at interim analysis 2. However, findings supporting a potentially enriched response in subjects with LAG-3 positive tumor in arm1, warrant further development of the LAG525 plus spartalizumab combination in a LAG-3 positive selected patient population (refer to the rationale for arm 1A in [Section 2.4.1.1](#)).

Arm 2 (capmatinib plus spartalizumab) and arm 3 (canakinumab plus spartalizumab) were declared futile based on protocol specific criteria at interim analysis 1 and enrollment was consequently stopped for these arms. Arm 4 (ribociclib plus spartalizumab) was declared futile at interim analysis 3 after the enrollment in this arm was stopped at 44 subjects due to COVID-19 situation.

## Part 2: Expansion phase

Only combinations arms that have met the pre-specified criteria defined in [Section 4.2](#) and [Section 10](#) will be opened for enrollment in part 2.

[figure not shown]
Exact randomization strategies in the situation when there is one (or more) arms open for enrollment in part 2 and there are still arms open for enrollment in part 1 will be determined at the time of the selection of the arm that will be expanded in part 2. Four factors will be considered at the time of opening an arm in part 2 to determine the exact randomization strategy and those are the following:

- Number of subjects enrolled in part 1 for the arm that meets criteria for expansion in part 2
- Number of subjects that will need to be enrolled in part 2 to have sufficient predictive power and alpha control
- Observed effect size (ORR) for the arm that meets criteria for expansion in part 2
- Observed effect size of other arms which are open for enrollment in part 1

Based on the sample size assumptions detailed in [Section 10.8.1](#) and the assumption that only one of the four initial arms will meet the criteria for efficacy and will be expanded to part 2, it is expected that approximately 50 subjects will be enrolled in the expansion phase.

The study design for the randomized section of this study is schematized in [Figure 4-1](#).

**Figure 4-1 Overview of study design for randomized section of the study**

#### 4.1.2 Non-randomized section of the study

Subjects meeting the eligibility criteria for arm 1A, as described in [Section 5](#), after the completion of screening procedures will be enrolled in this arm (in either part 1 or part 2) using the same Interactive Response Technology (IRT) system as used for the randomized section of the study.

Arm 1A will enroll up to approximately 100 subjects in total with LAG-3 positive melanoma (for both parts of the study) unless further exploration of this arm is stopped after 1st or 2nd interim analysis: 20 subjects in the selection phase and up to approximately 80 subjects in the expansion phase.

##### Part 1: Selection phase

After approval of protocol amendment 5, the following non-randomized combination arm will be opened for enrollment in part 1:

- **Arm 1A:** LAG525 600 mg i.v. Q4W and spartalizumab 400 mg i.v. Q4W, assessed in a population selected based on the LAG-3 status of their tumor.

Twenty (20) subjects will be treated in arm 1A in part 1. One interim analysis on these 20 subjects will be conducted as described in [Section 4.2.2](#) to determine whether the efficacy probabilistic threshold is crossed for arm 1A and thus arm 1A may be expanded to part 2 or be dropped for futility.

##### Part 2: Expansion phase

Arm 1A will be opened for enrollment in part 2 only if the pre-specified criterion defined in [Section 4.2.2](#) and [Section 10.4.2.2](#) for this arm is met.

Based on the sample size assumptions detailed in [Section 10.8.2](#), it is expected that up to approximately 80 subjects will be treated in arm 1A in the expansion phase, unless further exploration of this arm is stopped after 2nd interim analysis.

A second interim analysis will be conducted based on data from 20 additional subjects treated in expansion phase (i.e. 40 subjects in total combined with part 1 subjects) as described in [Section 10.4.2.2](#) to support and inform decision-making on whether the arm 1A will be further explored or dropped for futility.

Enrollment may be held after 20 subjects are treated in part 2 until the outcome of the 2nd interim analysis is available.

Novartis may decide at any time during the study to prematurely stop enrollment in arm 1A for any reason. The study design for the non-randomized section of the study is schematized in [Figure 4-2](#).

**Figure 4-2 Overview of study design for non-randomized section of the study**

#### **4.1.3 Subject-level study design (common to randomized and non-randomized sections of the study)**

Subjects in both part 1 and part 2 will undergo the same study periods as described below and in [Figure 4-3](#) and will have assessments performed as described in [Table 7-2](#):

[figure not shown]
##### **Screening period**

Subjects must sign the provided IRB/EC approved study informed consent form (ICF) prior to any study specific screening procedure. Refer to [Section 7.1.2](#) for details on screening procedures and timing.

##### **Treatment period**

The treatment period begins when the first dose of study treatment is administered to the subject (on Day 1 of Cycle 1 [C1D1]), maximum 3 days after date of randomization/enrollment.

After randomization in one of the open arms (or enrollment in arm 1A) in part 1 or part 2, subjects will receive the study treatment corresponding to their arm on a 28-day cycle basis as described in [Section 6](#) until disease progression per RECIST v1.1 by local assessment, unacceptable toxicity, start of subsequent anti-cancer therapy, withdrawal of consent, investigator's decision, lost to follow-up, death, or study is terminated by the sponsor. Subjects will be followed as per the schedule of assessments defined in [Section 7](#).

The first RECIST v1.1 tumor assessment is scheduled 12 weeks after the date of randomization (or after the date of first dose of study treatment in arm 1A) and subsequent tumor assessments are detailed in [Section 7.2.1](#).

Subjects may continue study treatment beyond disease progression by RECIST v1.1 if considered to be in the best interest of the subject and as long as all the protocol-specific criteria defined in [Section 6.1.5.1](#) are met. In this case, the subject will continue assessments as defined in [Section 7](#).

### **End of Treatment**

Subjects should be scheduled for an End of Treatment (EoT) visit (refer to [Section 7.1.5](#) for assessments to be performed) within 7 days after permanent discontinuation of study treatment for any reason (i.e. within 7 days after the last dose of the last study drug or after the date when decision was made to permanently discontinue both study drugs/the last study drug).

### **Safety follow-up**

[figure not shown]
After study treatment discontinuation, all subjects must be followed for safety evaluations up to 150 days after the last dose of study treatment as outlined in [Section 7.1.7](#).

### **Efficacy follow-up**

[figure not shown]
In parallel with the safety follow up, subjects who have permanently discontinued study treatment for any reason other than disease progression by RECIST v1.1 will continue tumor assessments as outlined in [Section 7.1.8](#) until documented disease progression per RECIST v1.1 by local assessment, withdrawal of consent, lost to follow-up, death, or study is terminated by the sponsor. Every effort will be made to continue collection of tumor assessments even after start of another anti-cancer therapy for subjects that have not progressed.

### **Survival follow-up**

Survival status and all subsequent anti-cancer therapies initiated after study treatment discontinuation (radiotherapies, surgeries and medications, including regimen number, names of all medications received within each regimen and start/end dates for each medication) will be collected as outlined in [Section 7.1.9](#) until death, withdrawal of consent, lost to follow-up or end of study.

**Figure 4-3 Overview of study design at subject level.**

## 4.2 Timing of interim analyses and design adaptations

### 4.2.1 Randomized section of the study

The first interim analysis will be conducted in part 1 after approximately 10 subjects have been enrolled in each of the first three arms (arm 1, arm 2 and arm 3) and have completed the second post-baseline tumor assessment or have discontinued study treatment prior to completing the second post-baseline tumor assessment. The requirement to have at least 10 subjects in each arm is based on simulations showing that 10 is the minimal number of subjects to be able to declare futility as per decision rules presented below and also in [Section 10.4.2.1](#).

[figure not shown]
Subsequent interim analyses in part 1 will be conducted approximately every 20 weeks thereafter (since the first post-baseline assessment occurs at week 12, and the next post-baseline assessment occurs 8 weeks later) until sufficient subjects have been enrolled to assess if a combination is futile or meets the criteria for expansion in part 2. The first interim analysis for arm 4 (ribociclib and spartalizumab) will be synchronized with the subsequent planned interim analyses for the other arms and will occur when at least 10 subjects have been randomized to that arm and have either completed two post-baseline tumor assessments or have discontinued study treatment. Each interim analysis will be linked to a clinical decision point. Although the formal interim decisions rules and statistical thresholds (described in the paragraph below and in [Section 10](#)) are based on the observed confirmed ORR, all available efficacy, safety and biomarker data will be considered at each decision point to determine arms which are (1) considered futile, (2) will be expanded in part 2, or

(3) will continue enrollment in part 1 (until a maximum of 45 subjects). [REDACTED] [REDACTED] Figure 4-4 presents pre-specified criteria for decision-making.

Statistical thresholds for efficacy and futility to be used at each interim analysis are defined as  $P(\text{true ORR} \geq 20\%) \geq 70\%$  and  $P(\text{true ORR} \leq 15\%) \geq 70\%$ , respectively. These statistical thresholds were chosen based on simulations so that clinically meaningful ORR thresholds of 10% for futility and 25% for efficacy are achieved with high probability (as presented in Table 10-10 in Section 10.8). The targeted ORR of 25% is deemed to be transformative in this population, since treatments are very limited for subjects who have not responded to, or progressed on the approved therapies for unresectable or metastatic melanoma. The probabilities will be calculated at each decision point for each arm based on observed confirmed ORR. Further details are provided in Section 10.4.2.1.

No interim analysis is planned for part 2.

**Figure 4-4** Pre-specified criteria for decision making at each decision point (interim analysis) in part 1 to determine expansion in part 2 or drop of a combination arm

[figure not shown]

Of note, interim analyses will continue to be performed in the randomized section of the study at the pre-defined frequency until a clinical decision (e.g. arm declared futile or efficacy probabilistic thresholds crossed) on each arm in part 1 has been made. Even if declared futile, combination arms will be analyzed at subsequent interim analyses until all subjects have been reported at least once (i.e. had a minimum follow-up of 20 weeks). Additional descriptive analyses may be performed if required.

#### 4.2.2 Non-randomized section of the study

The first interim analysis will occur in part 1 once all 20 subjects have been treated in arm 1A (in part 1) and followed up for at least two post-baseline efficacy assessments or have discontinued study treatment.

If arm 1A is expanded in part 2, the second interim analysis will be conducted once 20 additional subjects (i.e. 40 subjects in total combined with part 1 subjects) have been treated in the expansion phase and followed up for at least two post-baseline efficacy assessments or have discontinued study treatment.

Each interim analysis will be linked to a clinical decision point. Although the formal interim decisions rules and statistical thresholds (described in the paragraph below and in [Section 10](#)) are based on the observed confirmed ORR, all available data will be considered at this decision point to determine if the arm 1A is (1) considered futile, or (2) the efficacy probabilistic threshold is crossed and arm 1A may be expanded in part 2/may continue enrollment in part 2 at time of first interim analysis/2nd interim analysis respectively.

Statistical thresholds for efficacy and futility to be used is defined as  $P(\text{true ORR} \geq 20\%) > 70\%$  and  $P(\text{true ORR} \geq 20\%) \leq 70\%$ , respectively. These statistical thresholds were chosen so that there is a sufficient efficacy signal observed before advancing this arm to the expansion phase and to ensure that if the true underlying ORR is 30% (clinically meaningful ORR) then the probability of crossing the threshold is sufficiently large (as presented in [Section 10.4.2.2](#)). The targeted ORR of 30% is deemed to be clinically meaningful and transformative in this selected patient population, where the ORR would be expected to be higher than in a non-selected population. The probabilities will be calculated based on observed confirmed ORR. Further details are provided in [Section 10.4.2.2](#).

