### **7.2.1.2 Post-baseline imaging assessments**

Imaging assessments as described in [Table 7-3](#) should be performed at the time points specified using the same imaging modality used at baseline, irrespective of study treatment interruption or actual dosing (see [Table 7-2](#)). Imaging assessments for response evaluation will be performed 12 weeks ( $\pm 7$  days) after the date of randomization (or after the date of first dose of study treatment in arm 1A), then every 8 weeks ( $\pm 7$  days) until 52 weeks after randomization/date of first dose of study treatment in arm 1A, and every 12 weeks ( $\pm 7$  days) thereafter until disease progression per RECIST 1.1 (as assessed by the investigator), death, lost to follow-up or withdrawal of consent. Imaging assessments should be scheduled using the randomization date (or after the date of first dose of study treatment in arm 1A) as the reference date (not the date of the previous tumor assessment), and should be respected regardless of whether treatment with study treatment is temporarily withheld or unscheduled assessments performed.

An additional tumor assessment must be performed to confirm response (complete response CR or partial response PR) as per RECIST v1.1, no less than 4 weeks after the criteria for response are first met.

For subjects who discontinue study treatment without disease progression per RECIST v1.1 (as assessed by the investigator), imaging assessments must be performed as part of efficacy follow up as described in [Table 7-2](#) and [Table 7-3](#) until disease progression per RECIST v1.1 (as assessed by the investigator), death, lost to follow-up or withdrawal of consent.

Every effort will be made to continue collection of tumor assessments even after the start of subsequent anti-cancer therapy for subjects that have not progressed.

For all subjects (including those who continue study treatment beyond disease progression per RECIST v1.1), at least two additional tumor assessments that are at least 4 weeks apart are recommended subsequent to disease progression per RECIST v1.1 [REDACTED] no less than 4 weeks after criteria for disease progression per RECIST v1.1 are first met. Tumor assessments after start of new anti-cancer therapy are recommended.

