**Table 10-4 Probabilities thresholds used to declare efficacy or futility for arm 1A**

Decision rule	Action
$P(\text{ORR} \geq 20\%) \leq 70\%$	Drop arm for futility
$P(\text{ORR} \geq 20\%) > 70\%$	Efficacy signal - Consider advancing arm to expansion phase (part 2)

The efficacy probabilistic threshold and decision criterion was determined so that a sufficient signal of efficacy needs to be observed before advancing this arm to the expansion phase and to ensure that if the true underlying ORR is 30% (clinically meaningful ORR) then the probability of crossing the threshold is sufficiently large (refer to [Table 10-12](#)).

To calculate the posterior probabilities, a beta-binomial posterior distribution will be used as shown below:

$$p \sim \text{beta}(y + 1, n - y + 1)$$

Where  $y$  is the number of confirmed responses in arm 1A and  $n$  is the number of subjects treated. In calculation of the posterior distribution, uninformed prior Beta[1,1] will be taken into account. The posterior probability will be calculated based on the observed ORR using RECIST v1.1 criteria at interim analysis as described in [Section 10.7.2](#).

The final decision on whether the arm will be selected for advancement to the expansion phase will primarily be based on the observed ORR using decision rule described above but other efficacy (in particular duration of response), safety, and biomarker data will be considered as well. Novartis may decide to not expand the arm despite the efficacy probability threshold crossed.

With 20 treated patients, 5 or more responders need to be observed to meet the efficacy probabilistic threshold as illustrated in [Table 10-5](#).

**Table 10-5 Posterior probability ORR≥20% given observed ORR at time of 1st interim analysis of selection phase**

# of Responders out of 20	ORR observed (%)	PP(ORR≥20%   observed ORR) (%)
0	0	0.9
1	5	5.8
2	10	17.9
3	15	37.0
4	20	58.6
5	25	76.9
6	30	89.1
7	35	95.7
8	40	98.9

# of Responders out of 20	ORR observed (%)	PP(ORR≥20%   observed ORR) (%)
9	45	99.6
10	50	99.9

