### **10.4.3 Handling of missing values/censoring/discontinuations**

For the computation of ORR, all confirmed responses (CR or PR) reported up to the analysis cut-off will be included. Subjects with no valid radiological assessment or unconfirmed responses will be considered as non-responders. Subjects who were non-responders before initiation of subsequent anti-cancer therapy will still be non-responders. In particular, subjects with CR or PR at the last radiological assessment prior to cut-off and no response at the previous assessment are by definition unconfirmed and will be considered as non-responders for the primary analysis.

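### Arm 1A futility looks can open before week-20 responses are confirmed, so Table 10-12 is an upper bound that assumes no response is pending

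*Protocol*

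**What the plan says.** **When a look opens.** Section 4.2.2 sets the first look after 20 treated subjects and the second after 40, once those subjects have been "followed up for at least two post-baseline efficacy assessments or have discontinued study treatment". Section 10.7.2 repeats the rule. Section 7.2.1.2 puts the first two scans at weeks 12 and 20.

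**What is counted.** Section 4.2.2: "The probabilities will be calculated based on observed confirmed ORR". In Section 10.4.2.2, under Table 10-4, y "is the number of confirmed responses in arm 1A and" n "is the number of subjects treated", with a Beta(1,1) prior.

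**What confirmation needs.** Section 7.2.1.2 requires a further tumor assessment "no less than 4 weeks after the criteria for response are first met".

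**How an unconfirmed response is handled.** Section 10.4.3: "Subjects with no valid radiological assessment or unconfirmed responses will be considered as non-responders". It adds that "subjects with CR or PR at the last radiological assessment prior to cut-off and no response at the previous assessment are by definition unconfirmed"; that sentence goes on to limit itself to the primary analysis.

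**What follows from the count.** Table 10-4 has two outcomes. A posterior probability of ORR ≥20% that exceeds 70% is an efficacy signal; anything else is futility. Section 10.4.2.2 translates this into at least 5 of 20 and at least 9 of 40.

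**The concern.** The trigger and the endpoint do not fit together in time. A response first seen at week 12 can be confirmed at the week-20 scan. A response first seen at week 20 completes the subject's two-scan requirement on that day, but cannot be confirmed until week 24 at the earliest. Nothing in Sections 4.2.2, 10.4.2.2 or 10.7.2 makes the cut-off wait, so the subject can enter the count as a non-responder.

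The error runs one way, towards dropping an active arm. Arms 1 to 4 had a zone between futility and efficacy in which enrollment continued (Table 10-1). Arm 1A has no such zone, so a single pending response can decide the look. A futile result means no expansion at the first look and a stop to enrollment at the second. Section 10.8.2 supports the sample size with power above 70%, and Table 10-12 gives 72.1%, which leaves little room for loss.

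**Working it through.** **1. The boundaries.** The posterior is Beta(y+1, n−y+1), and the quantity needed is P(ORR ≥ 20%).

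| y/n | P(ORR ≥ 20%) | Decision (>70%) |
|---|---|---|
| 5/20 | 76.9% | go |
| 4/20 | 58.6% | futile |
| 9/40 | 70.4% | go |
| 8/40 | 56.2% | futile |

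These match Tables 10-5 and 10-6. Each boundary turns on one response.

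**2. The plan's own operating characteristics.** Let X be the responders among the first 20, Y those among the next 20 and Z those among the last 60, all binomial with p = 0.30. The final rule is at least 23 of 100, because the exact 95% lower bound is 15.2% at 23.

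- Pass the first look: P(X ≥ 5) = 76.2%
- Pass both looks: P(X ≥ 5 and X+Y ≥ 9) = 73.5%
- Positive study: P(X ≥ 5, X+Y ≥ 9 and X+Y+Z ≥ 23) = 72.1%

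All 36 percentages in Table 10-12 reproduce to 0.1 point, provided every eventual confirmed response is already counted at each look. The table therefore makes no allowance for pending responses.

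**3. Allowing for pending responses.** Let f be the fraction of eventual confirmed responders who are still unconfirmed in the cohort being read. The protocol gives no value for f, so a range is assumed. The first 20 subjects are taken as mature by the second look.

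- The count at the first look is Binomial(20, 0.30(1−f)). For f = 10%: P(count ≥ 5 | 20, 0.27) = 66.2%.
- At the second look X is counted in full, and each of the Y responders is counted with probability 1−f.
- The final rule uses all responses, because every subject then has at least 9 months of follow-up.

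| f | Pass first look | Pass both | Positive study |
|---|---|---|---|
| 0 | 76.2% | 73.5% | 72.1% |
| 2.5% | 73.9% | 71.1% | 69.8% |
| 5% | 71.5% | 68.6% | 67.4% |
| 10% | 66.2% | 63.1% | 62.1% |
| 20% | 54.4% | 51.1% | 50.4% |

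**4. Which values of f are plausible.** Only subjects near their second scan at the cut-off are exposed. Staggered entry was simulated with exponential gaps between entries, the cut-off when the last subject reaches week 20, and true ORR 30%. Accrual and response timing are assumptions.

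| Accrual per month | Responders first seen at week 20 | Confirmed after | Pass first look | Pass both | Positive study |
|---|---|---|---|---|---|
| 1 | 10% | 4 weeks | 75.4% | 72.6% | 71.2% |
| 2 | 20% | 4 weeks | 73.6% | 70.8% | 69.5% |
| 4 | 20% | 4 weeks | 71.8% | 68.9% | 67.7% |
| 8 | 20% | 4 weeks | 68.1% | 65.0% | 64.0% |
| 8 | 20% | 8 weeks | 60.0% | 56.7% | 55.9% |

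The average pending share is 2.8% in the second row, 4.7% in the third, 8.4% in the fourth and 15.5% in the last.

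**The case against.** **The exposed group may be small.** Two scans is a minimum, and earlier entrants will have more. The protocol gives no accrual rate for arm 1A, but it hints at a slow one. Section 10.8.1 assumes 8 subjects per month for the randomized arms, and Section 2.4.1.1 reports 4 LAG-3 positive subjects of 35 in arm 1. That would imply about 8 × 4/35 = 0.9 per month, though some samples were not evaluable and the set of sites may differ. At 0.9 per month with 20% of responders first seen at week 20, about 1.8% to 2.7% would be pending, and the first-look pass probability would be 74.6% or 73.7% instead of 76.2%. This stands, and it argues against treating a 10% or 20% pending share as the expected case.

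**The decision is not mechanical.** Section 4.2.2 says all available data will be weighed, so a pending partial response at 4/20 would be visible. This mitigates the problem without curing it. No rule covers pending responses, Section 10.4.2.2 says an arm below the threshold will be declared futile, and the only departure it spells out is declining to expand after the threshold is crossed.

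**Stronger readings that the documents do not support.**
- A reader might infer that treated but unscanned subjects swell the denominator, since n is defined as subjects treated and the hold is optional ("Enrollment may be held after 20 subjects are treated in part 2"). But n is fixed at 20 and 40 by Section 4.1.2, Section 10.4.2.2 and Tables 10-5 and 10-6, and part 2 opens only after the first look.
- A reader might infer that the discontinuation clause should be replaced, because scans continue after treatment stops. By default, however, Appendix 2 (Section 14.2.3.1) leaves assessments more than 30 days after the last dose out of best overall response, so many of those scans would not count.

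**Conclusion.** The mismatch is real, and its direction is certain: followed as written, the rule can only lower the chance that an active arm passes. Its size is not known. Table 10-12 is arithmetically correct but is an upper bound, reached only if no response is pending at either look. A reader might conclude that the tabulated power cannot be achieved at all. The documents do not support that, because with slow accrual and mostly early responses the loss is around 1 to 3 points.

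The claim of power above 70% nevertheless has little slack: 2.5% pending is enough to bring it to 69.8%. Falls to about 62% or 50% need 10% or 20% of eventual responders to be pending across the cohort being read. In the staggered-entry runs, shares of that order arose mainly at 4 to 8 subjects per month with late responders. These results rest on a true ORR of 30%, assumed pending shares and the first 20 subjects being mature by the second look. The type I error is not threatened.

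**What to change.** In Sections 4.2.2, 10.4.2.2 and 10.7.2, state that the interim data cut-off (or the futility call) waits until every subject with an unconfirmed CR or PR at the second scan has had the confirmatory scan already required by Section 7.2.1.2. Next to Table 10-12, state that its figures assume no pending responses at either look.

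The cost is amendment wording and a delay that arises only when a confirmation is pending: about 4 weeks if the scan is done at the earliest time (week 24), or 8 weeks if it is left to the next scheduled scan (20 + 8 = week 28). No additional scans are needed. The denominators of 20 and 40 and the discontinuation clause can stay as they are.
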